6.2.6 Blood submission for pharmacogenetics (A011203-PP)

All patients treated with Z-Endoxifen HCl or tamoxifen, who have consented, to A010203-PP will provide a single blood sample for **pharmacogenetic** analysis as follows:

Day 1, Cycle 1 prior to treatment **or at any time after Pre-registration**, collect a 10-mL sample of blood in an EDTA (Purple top) tube. The tube should be inverted approximately 8-10 times to mix the EDTA. Refrigerate sample until shipping. The sample should be placed in a biohazard bag and shipped the same day on a cold pack by overnight to:

Alliance Biorepository at Ohio State University
The Ohio State University
Innovation Centre
[name]
[name]
[contact] [contact]

Shipment on Monday through Thursday by overnight service to assure receipt is encouraged.

6.2.7 Blood submission for pharmacokinetics for patients who have consented (A011203-PP1)

For all patients who have consented to A011203-PP, blood samples for **pharmacokinetics** will be collected in all patients treated with Z-Endoxifen HCl or tamoxifen, according to the following schedule:

- Cycle 1 Day 1: Prior to drug administration
- Cycle 1 Day 1: 2-4 hours after drug administration
- Cycle 1 Day 1: 4-6 hours after drug administration **Note:** Do not draw samples within 2 hours of each other.)
- Cycle 1 Day 2: Prior to drug administration
- End of Cycle 2, (prior to the start of Cycle 3) prior to drug administration
- End of Cycle 8, (prior to the start of Cycle 9) prior to drug administration
- At the time of disease progression

For those patients with crossover from tamoxifen to Z-Endoxifen HCl, pharmacokinetic samples will be collected as follows:

- End of Cycle 2, (prior to the start of Cycle 3) prior to drug administration
- End of Cycle 8, (prior to the start of Cycle 9) prior to drug administration
- At the time of disease progression

Notes: 1) The patient must record the time of day that the dose was taken on the previous day. 2) The patient should be reminded not to take the dose on this day until after the blood sample is drawn.)

NOTE: Samples are light sensitive. Use amber tubes or cover tubes with aluminum foil to prevent exposure to light.

For each time point, 6mL blood sample will be collected in 6mL EDTA (purple top) tube, wrapped in aluminum foil and immediately cooled in an ice water bath. Blood must be processed for plasma isolation within 20 minutes of collection.

Blood will be subjected to centrifugation (2,000 rpm for 10 minutes) in a refrigerated centrifuge kept at 4°C. Following centrifugation, the plasma will be transferred to a polypropylene tube, capped, wrapped in aluminum foil and immediately frozen at -70°C.

Tube labels must contain the following data:

- Alliance protocol number (A011203), Alliance patient ID number, patient's initials and date and type of specimen collected (plasma).
- Date, cycle number and time of collection (i.e. pretreatment, 1, 2, and 4 hours after the oral dose)

These same data should be recorded in nurse's notes, on the Alliance A011203 Pharmacokinetics Study Form that will be uploaded into RAVE. A copy of the form should be sent with the samples.

Send frozen plasma samples on dry ice via overnight courier to the Alliance Pathology Coordinating Office.

7.0 TREATMENT PLAN/INTERVENTION

Patients will be randomized with equal probability to receive daily treatment with Z-Endoxifen HCl or tamoxifen. Treatment on Arms I and II will continue until disease progression or unacceptable adverse event.

Protocol treatment is to begin \leq 14 days of registration/randomization in order to allow for Z-Endoxifen HCl to arrive for patients assigned to Arm I.

7.1 Arm I Z-Endoxifen HCl

Agent	Dose	Route	Day	Retreatment Cycle
Z-Endoxifen HCl	80 mg	Oral (2 x 40mg capsule)	Days 1-21	Every 21 days (+/- 3 days)

1. Patients will take Z-Endoxifen HCl on an empty stomach (1 hour before or 2 hours after meals).
2. Patients should be instructed that the Z-Endoxifen HCl should be refrigerated. The Z-Endoxifen HCl should be dispensed with a cooler pack that the patient can use to transport this study medication.

7.2 Arm II Tamoxifen

Agent	Dose	Route	Day	Retreatment Cycle
Tamoxifen	20 mg	Oral (1 x 20 mg tablet)	Days 1-21	Every 21 days (+/- 3 days)

1. Patients will take tamoxifen without regard to meals.

7.3 Crossover to Z-Endoxifen HCl for Arm II Patients at Disease Progression

Please note that patients who opt to cross over should be re-registered to the study within 14 days of progression documentation.

Patients with measureable disease who meet the RECIST criteria for disease progression and patients with bone only disease who progress during tamoxifen treatment may switch to Z-Endoxifen HCl.

Those patients with both non-measurable disease and bone metastases are also eligible to cross over to Z-Endoxifen HCl.

Palliative radiation, if administered, should be completed prior to re-registration. Note that imaging studies obtained at the time of disease progression on Tamoxifen treatment Arm should be used to obtain the baseline tumor measurements for the Z-Endoxifen HCl crossover phase. These images must have been taken no more than 28 days prior to re-registration. Also, lesions that have been irradiated must not be used to evaluate tumor response to Z-Endoxifen HCl.

Z-Endoxifen HCl treatment should start no later than 28 days after documentation of progression.

Agent	Dose	Route	Day	Retreatment Cycle
Z-Endoxifen HCl	80 mg	Oral (2 x 40mg capsule)	Days 1-21	Every 21 days (+/- 3 days)

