3.0 PATIENT SELECTION

For questions regarding eligibility criteria, see the Contact Information page. Please note that the Study Chair cannot grant waivers to eligibility requirements.

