3.3 Registration Eligibility Criteria

Registration must be completed within 28 days of Pre-registration

3.3.1 Patients with either measurable disease as defined by RECIST criteria (See Section 11.0) or bone only disease are eligible. Note: Those patients with both non-measurable disease and bone metastases are eligible.

- Non-measurable bone only disease: Non-measurable bone only disease may include any of the following: blastic bone lesions, lytic bone lesions without a measurable soft-tissue component, or mixed lytic-blastic bone lesions without a measurable soft-tissue component.
- Lytic bone lesions, with an identifiable soft tissue component, evaluated by CT or MRI, can be considered as measurable lesions if the soft tissue component otherwise meets the definition of measurability previously described.

3.3.2 No tumors involving spinal cord or heart.

3.3.3 No visceral crisis, lymphangitic spread or known brain metastases: Visceral crisis is not the mere presence of visceral metastases, but implies severe organ dysfunction as assessed by symptoms and signs, laboratory studies, and rapid progression of disease.

3.3.4 Histologic confirmation, from the A011203 Pre-registration biopsy, by institutional/local pathologist of either locally advanced or metastatic breast cancer that is estrogen receptor positive and HER2 negative.

Those patients with bone only disease with either no tumor or insufficient tumor for ER/PR and HER2 staining after the bone biopsy are still eligible to participate in this study.

3.3.5 Estrogen receptor positive disease is defined as > 10% nuclear staining.

3.3.6 **HER2 Negative Disease as per 2013 ASCO/CAP guidelines, one of the following must apply:**

- 1) 0 or 1+ by IHC and not amplified by ISH
- 2) 0 or 1+ by IHC and ISH not done
- 3) 2+ by IHC and not amplified by ISH or
- 4) IHC not done and not amplified by ISH

3.3.7 **None of the following therapies are allowed prior to registration*:**

- Chemotherapy \leq 2 weeks
- Immunotherapy \leq 2 weeks
- Biologic therapy \leq 2 weeks
- Hormonal therapy \leq 2 weeks
- Monoclonal antibodies \leq 2 weeks
- Radiation therapy \leq 2 weeks
- Anti-Her-2 or other “targeted” (e.g. mTOR) therapy \leq 2 weeks

*Note: Any toxicities derived from these therapies must be \leq grade 2 prior to starting study therapy.

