4.4 Pre-registration Requirements

- Patient pre-registration can occur only after screening evaluation is complete, pre-registration eligibility criteria have been met, and the study site is listed as "approved" in the CTSU RSS.
- **Informed consent:** the patient must be aware of the neoplastic nature of his/her disease and willingly consent after being informed of the procedure to be followed, the experimental nature of the therapy, alternatives, potential benefits, side-effects, risks, and discomforts. Current human protection committee approval of this protocol and a consent form is required prior to patient consent and pre-registration.

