4.9 Re-registration at the Time of Progression

Patients who meet the RECIST criteria for disease progression during tamoxifen treatment may switch to Z-Endoxifen HCl until disease progression is documented. Please note that patients who opt to cross over must be re-registered to the study within 14 days of progression documentation.

Re-registration procedures:

OPEN may be accessed at <https://open.ctsu.org>, from the OPEN tab on the CTSU website at <https://www.ctsu.org>.

To enroll a patient within OPEN, institution staff must have:

1. A valid and active CTEP-IAM account. This is the same user ID and password used for CTSU's website (for more information see https://www.ctsu.org/public/CTEP-IAM_Factsheet.pdf).
2. Enrollment of patients on Alliance A011203 coordinated protocols requires a "Registrar" role in the ALLIANCE roster. Assignment of the "Registrar" role is managed through the Alliance Central Office.

The OPEN system will provide the registering site with a printable confirmation of re-registration. Please print the confirmation for your records. Further instructional information is provided on the CTSU members' website OPEN tab, or within the OPEN URL. For any additional questions, contact the CTSU Help Desk at [name], or [contact].

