5.0 STUDY CALENDAR

Pre-Study Testing Intervals for all patients

- To be completed ≤ 14 DAYS before Pre-registration: All laboratory studies, history and physical.
- To be completed ≤ 28 DAYS before registration: Any imaging utilized for tumor measurement per protocol.

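### Crossover to Z-Endoxifen HCl 80 mg does not re-apply the entry limits on recent DVT/PE or on laboratory values

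*Combined protocol and SAP*

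**What the plan says.** Section 7.3 opens crossover to tamoxifen patients with measurable disease who progress by RECIST, and adds that "patients with bone only disease who progress during tamoxifen treatment may switch to Z-Endoxifen HCl". Patients with both non-measurable disease and bone metastases are included. Any palliative radiation must be finished, the progression images may be at most 28 days old at re-registration, and dosing should begin within 28 days of documented progression. The dose is 80 mg daily, the same as in Arm I. Section 3.2.9 excludes prior endoxifen, so this is the patient's first dosing with it.

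Section 12.3 gives the same permission as the patient's choice. Section 4.9 adds a time limit: "Please note that patients who opt to cross over must be re-registered to the study within 14 days of progression documentation". It then describes the registration step: "To enroll a patient within OPEN, institution staff must have" introduces a staff account and a Registrar role.

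Entry to the trial is worded differently. Section 4.4: "Patient pre-registration can occur only after screening evaluation is complete, pre-registration eligibility criteria have been met". Section 3.0: "Please note that the Study Chair cannot grant waivers to eligibility requirements". Those criteria include 3.2.13, which excludes a DVT or PE in the last 6 months but accepts older clots on maintenance anticoagulation. They also include 3.2.17: hemoglobin at least 9 g/dL, platelets at least 75,000/mm³, creatinine and bilirubin at most 1.5 x ULN, and AST at most 2.5 x ULN (5 x ULN with liver metastasis).

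For crossover, the Section 5.2 calendar schedules history, examination, performance status, blood pressure and labs at progression and on day 1 of each cycle. It states no value that must be met before starting.

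**The concern.** The clot and laboratory limits are applied once, before randomization. Tamoxifen is itself associated with venous thrombosis and pulmonary embolism (10.2.7), so a clot that would have barred entry can arise after that single check. The drug then started has its own signal. Grade 3-4 thromboembolic events are reported (10.1.7), the risk list in 9.3 includes thromboembolic event, and phase I recorded a cycle 1 dose-limiting pulmonary embolism in 1 of 6 patients at 60 mg, with none at higher dose levels (1.6). Read literally, Section 7.3 lets a patient with a pulmonary embolism last month begin 80 mg. What is at stake is patient safety at first exposure to an investigational agent.

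**Working it through.** The plan states no figure on this point, so the check is mainly a comparison of text, followed by three small calculations.

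**1. Conditions side by side**

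| Condition | Entry | Crossover (4.9, 7.3, 12.3) |
|---|---|---|
| Criteria must be met before registration | Yes (4.4), no waivers (3.0) | Not stated |
| No DVT/PE within 6 months | 3.2.13 | Not stated |
| Laboratory limits | 3.2.17, headed as initial values | Not stated; labs drawn, no threshold (5.2) |
| Disease status, imaging, timing | Yes | Yes |

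**2. What each safeguard does at re-registration**

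- 8.2.1 holds tamoxifen for grade 3-4 hepatic impairment, and a hold beyond 3 weeks ends protocol therapy. Under 12.3 a patient who stops for a reason other than progression goes to event monitoring, not crossover. This diverts some patients with severe liver abnormality. It does not reach a patient whose liver tests worsen as progression is documented. It requires no hold for a clot; stopping for other tamoxifen toxicity is left to the physician.
- 8.2.2 holds Z-Endoxifen HCl for grade 3-4 lymphopenia, thrombocytopenia or hypertriglyceridemia, with no attribution condition. Of the five 3.2.17 items, this touches only platelets, and it is written as a dose modification. Its other rule covers non-hematologic events attributed to Z-Endoxifen HCl, so a clot on tamoxifen does not trigger it.
- 12.7 stops therapy when the protocol is detrimental to health, and 3.1 asks for physician judgment at enrollment. Both are general and set no threshold.
- 13.1.7 counts toxicity by randomized arm, after it has occurred.

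None contains a DVT/PE rule or a starting laboratory limit for crossover.

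**3. Age of the last check against a limit**

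Inputs: labs and history at most "14 DAYS before Pre-registration: All laboratory studies, history and physical"; "Registration must be completed within 28 days of Pre-registration"; treatment starts within 14 "days of registration/randomization in order to allow for Z-Endoxifen HCl to arrive for patients assigned to Arm I".

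- First Arm I dose: at most 14 + 28 + 14 = 56 days.
- First crossover dose, for progression at the assumed 3.0-month median (about 91 days, 13.1.3): at least 91 days; at most 14 + 28 + 91 + 28 = 161 days.

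This is the age of the check against a threshold, not of the labs. Day 1 labs may be at most 21 days old in both cases (footnotes in 5.1 and 5.2), and neither set has a starting threshold.

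**4. Can progression plausibly fall inside the 6-month window?**

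Assume that the clot does not lead to stopping tamoxifen, and that the remaining time to a PFS event is exponential and independent of the clot. Then P(event within 6 months of the clot) = 1 − 2^(−6/median). If the crossover dose comes 28 days (0.92 month) after progression, 6 becomes 5.08.

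| Tamoxifen median | No delay | 28-day delay |
|---|---|---|
| 3.0 months (13.1.3) | 0.75 | 0.69 |
| 4.5 months (1.3.4) | 0.60 | 0.54 |
| 7.0 months (1.3.4) | 0.45 | 0.40 |

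These are upper values because PFS events include deaths. They show only that the window is long relative to time on tamoxifen.

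**5. How many could face the decision?**

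With λ = ln 2/3 = 0.231 per month, 15 months of accrual and 9 of follow-up, the tamoxifen event probability is 1 − (e^(−9λ) − e^(−24λ))/(15λ) = 1 − (0.1250 − 0.0039)/3.466 = 0.965, or 38.6 of 40 patients. Deaths without progression and refusals lower the number who could cross over.

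**The case against.** The strongest reply is that the protocol does not leave these patients unprotected, and that a 6-month bar is stricter than its own on-treatment rule. Under 8.2.2 an Arm I patient with a grade 3-4 clot attributed to Z-Endoxifen HCl may resume at 40 mg once it resolves within 21 days. After a clot on tamoxifen, tamoxifen may continue. The contrast between 4.4 and 4.9 is also thin, since the list in 4.9 concerns system access. Section 4.9 itself speaks of enrolling the patient, so the judgment asked for in 3.1 arguably applies again.

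Much of this stands. A reader might infer that nothing stands between a deteriorating patient and 80 mg; the safeguards listed in the working show otherwise, and they narrow the laboratory part in particular. The point therefore rests on what 7.3 and 12.3 leave out, not on the list in 4.9. The comparison with 8.2.2 shows that a milder clot rule could be defended, but it does not supply one. That rule requires resolution and a halved dose in a patient already exposed, whereas crossover starts the full dose and requires neither.

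**Conclusion.** The gap is real and should be closed for DVT/PE and laboratory values. As written, a patient with a recent clot who stays on tamoxifen and then progresses qualifies for first exposure at 80 mg, although the same history would have barred entry.

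Its size in patients is unknown. The documents give no clot rate on tamoxifen and no estimate of the risk that switching adds. The 40% to 75% range above might be read as a proportion affected or harmed. It is neither: it is conditional on a clot and on staying on tamoxifen, and crossover is optional.

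Three other stronger readings are not supported:

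- That every entry limit must be re-applied. For ECOG 0-2 and intercurrent illness (3.2.15, 3.2.12) the case is only consistency with entry.
- That the entry limits were specific to Z-Endoxifen HCl. They applied to both arms.
- That efficacy is compromised. Crossover follows the progression event, so the primary PFS comparison is unaffected.

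The conclusion assumes that no clinical checklist outside the protocol, such as the further registration instructions mentioned in 4.9, already imposes these limits.

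**What to change.** Add to 7.3, with cross-references in 4.9 and 12.3:

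*At re-registration the patient must have no DVT/PE within the past 6 months (3.2.13, with its anticoagulation note) and must meet the 3.2.17 laboratory limits on labs drawn within 21 days before starting Z-Endoxifen HCl.*

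Re-applying ECOG 0-2 and 3.2.12 is the sponsor's option. If the sponsor prefers a looser rule, for example for laboratory changes caused by progression, it should be written into 7.3 so that sites apply it alike.

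The cost is one sentence and two cross-references. No new test is needed, since 5.2 already schedules the history, examination and labs, and its footnote already uses the 21-day window. A few progressing patients would lose optional crossover, including some whose labs worsened through progression. That slightly changes who contributes to objective 2.2.3, the median PFS on Z-Endoxifen HCl after tamoxifen, and should be noted when that estimate is reported.

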7.4 Adherence

Patients will be taking oral medication at home, without direct supervision. Drug compliance will be monitored until the discontinuation of Z-Endoxifen HCl or tamoxifen using A011203 Study Medication Logs found in Appendix III. Patients should bring the Medication Log to each clinic visit. A study team member will review the Medication Log, discuss any missed dose or discrepancy and document it. The Medication Log should be returned to the treating institution and compliance must be documented in the medical record by any member of the care team.

8.0 DOSE AND TREATMENT MODIFICATIONS

8.1 Ancillary therapy, concomitant medications, and supportive care

8.1.1 Colony stimulating factors

Routine use of colony-stimulating factors (G-CSF or GM-CSF) are not allowed.

8.1.2 Concurrent therapy

Use of other concurrent chemotherapy or anti HER2 therapy, immunotherapy, radiotherapy, or any ancillary therapy considered investigational (utilized for a non-FDA-approved indication and in the context of a research investigation) is not allowed.

Patient who are receiving tamoxifen (Arm II), should not be treated with strong CYP2D6 inhibitors while receiving study treatment (see Section 10.1.5 and Appendix II).

8.1.3 Expected prominent symptoms

Vasomotor symptoms such as hot flashes, sweating, as well as other estrogen withdrawal symptoms including insomnia, depression, and weight gain may be prominent in patients receiving Z-Endoxifen HCl and/or tamoxifen. These symptoms should not be treated with dose reduction, rather, intervention with either an SSRI or SNRI that is not known to be a potent CYP2D6 inhibitor (see Appendix II for a list of acceptable drugs). CYP2D6 catalyzes the formation of endoxifen from tamoxifen. Among SSRIs studied, venlafaxine had the least effect on endoxifen levels. Paroxetine was the most potent inhibitor of CYP2D6, resulting in the lowest endoxifen concentrations.

If the patient continues to have symptoms that are bothersome, a 2nd line intervention such as gabapentin should be initiated. A dose reduction should be considered if these symptoms persist despite 2 lines of intervention.

8.1.4 Full supportive care

Patients should receive full supportive care while on this study. This includes blood product support, antibiotic treatment and treatment of other newly diagnosed or concurrent medical conditions and concomitant medications such as anti-diarrheals, analgesics and anti-emetics. All blood products and concomitant medications received from Cycle 1 Day 1 of study drug until 30 days after the final dose are to be recorded in the medical record.

8.1.5 Not to be considered for any other studies involving pharmacologic agents

Patients participating in this trial are not to be considered for enrollment in any other study involving a pharmacologic agent—(drugs, biologics, immunotherapy approaches, gene therapy) whether for symptom control or therapeutic intent.

8.1.6 Non-protocol hormones or other chemotherapeutic agents may not be administered. Patients who initiate such treatment will be removed from protocol therapy due to either concurrent medical condition or desire for alternative therapy, depending upon reasons these non-protocol medications were given.

8.1.7 Antiemetics may be used at the discretion of the attending physician.

8.1.8 Diarrhea: Diarrhea is not anticipated as a side effect from either drug. However, this could be managed conservatively with loperamide. The recommended dose of loperamide is 4 mg at first onset, followed by 2 mg every 2-4 hours until diarrhea free (maximum 16 mg/day).

In the event of grade 3 or 4 diarrhea, the following supportive measures are allowed: hydration, octreotide, and antidiarrheals.

If diarrhea is severe (requiring intravenous rehydration) and/or associated with fever or severe neutropenia (grade 3 or 4), broad-spectrum antibiotics must be prescribed. Patients with severe diarrhea or any diarrhea associated with severe nausea or vomiting **should be hospitalized** for intravenous hydration and correction of electrolyte imbalances.

8.1.9 Palliative radiation therapy may not be administered during protocol treatment. Patients who require radiation therapy during protocol treatment will be removed from protocol therapy due to disease progression.

